9.6 Statistical Methods

Statistical testing and inference for safety and immunogenicity analyses are described in Section 9.6.1 and Section 9.6.2, respectively. Section 9.6.3 describes how demographic and baseline characteristics will be summarized.

9.6.1 Statistical Methods for Safety Analyses

Safety and tolerability will be assessed by clinical review of all relevant parameters, including AEs, postvaccination temperatures, laboratory measurements, ECGs, and vital signs. For the 2-dose panels, summary of safety parameters following each dose separately will also be provided.

The analysis of AEs and postvaccination temperature measurements will follow a tiered approach (Table 9). The tiers differ with respect to the analyses that will be performed. Events (specific preferred terms as well as system organ classes) are either pre-specified as “Tier 1” endpoints, or will be classified as belonging to “Tier 2” or “Tier 3” based on the number of events observed.

Tier 1 Events

Safety events or AEs of special interest that are pre-identified constitute Tier 1 safety endpoints which will be subject to inferential testing for statistical significance with 95% CIs and corresponding p-values provided for the between-treatment differences in the proportion of participants with events.

No Tier 1 events are defined for this study.

This study will solicit for predefined injection-site and systemic AEs. However, as this is the first clinical study of V591, no data exists around which a comparative, data-driven safety hypothesis can be formulated and tested. As a result, the solicited injection-site and systemic AE reported in this study will be analyzed as Tier 2 events.

Tier 2 Events

Tier 2 parameters will be assessed via point estimates with 95% CIs provided for differences in the proportion of participants with events using the Miettinen and Nurminen method (1985) [Miettinen, O. and Nurminen, M. 1985].

Tier 2 events for this study include solicited injection-site AEs from Day 1 through Day 5 postvaccination, solicited systemic AEs from Day 1 through Day 14 postvaccination (Section 8.4.8.1). In addition, the broad AE categories consisting of the percentage of participants with any AE, any vaccine-related AE, any SAE, any vaccine-related SAE, any MAAEs, any ECI, and death will be considered Tier 2 events. Nonserious AEs will be followed for 28 days postvaccination, while SAEs will be followed through the duration of participation in the study. The proportion of participants with maximum temperature measurements meeting the Brighton Collaboration cut points (Days 1 to 14) will also be considered Tier 2 endpoints.

Adverse events (specific PTs as well as SOCs) will be classified as belonging to Tier 2 if at least 4 participants in any vaccination group exhibit the event. The threshold of at least 4 events was chosen because the 95% confidence interval for the between-group difference in percent incidence will always include zero when vaccination groups of equal size each have less than 4 events and thus would add little to the interpretation of potentially meaningful differences. Because many 95% CIs for Tier 2 events may be provided without adjustment for multiplicity, the CIs should be regarded as a descriptive measure supportive of safety review, not a formal method assessing the statistical significance of the between-group differences in AEs.

Tier 3 Events

Safety endpoints that are not Tier 1 or 2 events are considered Tier 3 events. Only point estimates by vaccination group are provided for Tier 3 safety parameters.

Table 9 Analysis Strategy for Safety Parameters

Safety Tier	Safety Endpoint	95% CI for Between-Group Comparison ^a	Descriptive Statistics
Tier 2	Solicited injection site AE (Days 1 to 5 after study intervention)	X	X
	Solicited systemic AE (Days 1 to 14 after study intervention)	X	X
	Any AE ^b	X	X
	Any Vaccine-Related AE ^b	X	X
	Any SAE ^b	X	X
	Any Vaccine-Related SAE	X	X
	Any MAAE	X	X
	Any ECI	X	X
	Death ^b	X	X
	Maximum temperature measurements meeting the Brighton Collaboration cut points (Days 1 to 14 after study intervention)	X	X
Specific AEs by SOC or PT (incidence ≥ 4 participants in at least one of the vaccination groups)	X	X	
Tier 3	Specific AEs by SOC and PT ^c (incidence < 4 participants in one of the vaccination groups)		X

AE = adverse event; CI = confidence interval; M&N = Miettinen and Nurminen; PT = preferred term; SAE = serious adverse event; SOC = system organ class; X = results will be provided.

^a These analyses will be performed using the M&N method.

^b These endpoints are broad AE categories. For example, descriptive statistics for the safety endpoint of “Any AE” will provide the number and percentage of participants with at least 1 AE.

^c Includes only those endpoints not prespecified as Tier 2 endpoints.

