3 HYPOTHESES, OBJECTIVES, AND ENDPOINTS

Healthy male participants and female participants between the ages of 18-55 years (inclusive) of age in Parts 1 and 2A (younger adults) and > 55 years of age in Part 2B (older adults)

Objectives	Endpoints
Primary	
To assess the safety and tolerability of V591 compared with placebo	
Solicited injection site adverse events from Day 1 through Day 5 after any study intervention
 
Solicited systemic adverse events from Day 1 through Day 14 after any study intervention
 
Unsolicited adverse events from Day 1 through Day 28 after any study intervention
 
SAEs from Day 1 throughout the duration of study
 
Medical attended AEs (MAAEs) collected from Day 1 throughout the duration of study

Secondary	
To compare the humoral immunogenicity of V591 with placebo at Day 29 (all panels) and Day 85 (Panels A, B, I, and J) or Day 197 (Panels K and L)	
Anti-SARS-CoV-2 spike serum neutralizing antibody (nAb) responses, as measured by Pseudo-virus Neutralization Assay (PNA)
 
Anti-SARS-CoV-2 spike Immunoglobulin G (IgG) responses, as measured by ELISA

To evaluate the humoral immunogenicity of V591 at all timepoints with serum collection	
Anti-SARS-CoV-2 spike serum nAb responses, as measured by Pseudo-virus Neutralization Assay (PNA)
 
Anti-SARS-CoV-2 spike IgG responses, as measured by ELISA

Tertiary/Exploratory	
To evaluate the immune response to of V591, including cell-mediated immunity	
PBMCs stimulated with SARS-CoV-2 Spike peptides for characterization of cell mediated immunity and serum to characterize the immune response to V591

[figure not shown]
Objectives	Endpoints
To characterize SARS-CoV-2 seroconversion rates among participants	Anti-SARS-CoV-2 N-protein IgG responses, as measured by immunoassay
To document confirmed diagnoses of SARS-CoV-2 infection among study participants	Laboratory confirmed diagnosis of SARS-CoV-2 infection reported as an ECI
To document study participants' exposures to confirmed SARS-CoV-2 cases	Known exposure to a confirmed case of active SARS-CoV-2 reported as an ECI

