4.2.1.3 Exploratory Endpoints

In accordance with regulatory guidance, this trial will endeavor to identify potential exposures and infections by SARS-CoV-2 amongst study participants. However, this clinical trial is not intended to interfere with local health practices and regulations regarding the management of confirmed or suspected SARS-CoV-2 infections. Study participants will be tested as appropriate according to local regulations and will receive any required medical care within their existing healthcare systems, please refer to Section 8.3.7 for further details.

Additional exploratory endpoints will include the follow assessments to assess the potential exposure to and infection by SARS-CoV-2 amongst study participants without potentially disrupting medical care:

- SARS-CoV-2 N protein specific antibody up to Study Day 534 as assessed by immunoassay. As the SARS-CoV-2 N protein is not included in the vaccine, infections in study participants seroconversion will identify asymptomatic and paucisymptomatic SARS-CoV-2 over the entire course of the study.
- Any laboratory confirmed diagnosis of SARS-CoV-2 infection (PCR or antigen based) and any resulting clinical sequelae will be reported as an ECI in study participants throughout the duration of the study.
- Known exposure to a confirmed case of active SARS-CoV-2, defined as individual who has had close contact (< 1.5 meters for ≥ 15 minutes), will be reported as an ECI in study participants throughout the duration of the study.

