8.3.7 Monitoring for SARS Cov-2 Exposure and COVID-19 Disease

As outlined in Section 4.2.1.3, this trial intends to identify potential exposures and confirmed infections by SARS-CoV-2 amongst study participants.

Study participants will be educated to recognize and report symptoms that may be related to SARS-CoV-2 infection and will be instructed to contact the site via phone in case of suspected SARS-CoV-2 infection (if severe symptoms are reported the participant will be instructed to seek urgent medical attention). The Investigator will facilitate the study participant receiving medical care as appropriate based on their clinical judgement, including arranging a nasopharyngeal PCR testing for acute disease. No more than 3 days should transpire between the subject contacting the clinical site and the arrangement of a medical care visit by the investigator.

Trial participants will be educated at regular intervals during in person visit to recognize and report the following potential SARS-CoV-2 symptoms based on current CDC guidance (<https://www.cdc.gov/coronavirus/2019-ncov/symptoms-testing/symptoms.html>).

- Fever or chills
- Cough

- Shortness of breath or difficulty breathing
- Fatigue
- Muscle or body aches
- Headache
- New loss of taste or smell
- Sore throat
- Congestion or runny nose
- Nausea or vomiting
- Diarrhea

The Investigator will endeavor to collect detailed data on confirmed COVID-19 cases including the onset of specific symptoms, duration of symptoms, hospitalization (if any), and COVID-19 will be classified as severe or non-severe based on the FDA's "Development and Licensure of Vaccines to Prevent COVID-19, Guidance for Industry"

For the purposes of this study, a virologically confirmed SARS-CoV-2 infection is defined as any study participant with positive SARS-CoV-2 PCR test.

Severe COVID-19 is defined as:

Virologically confirmed SARS-CoV-2 infection with any of the following:

- Clinical signs at rest indicative of severe systemic illness (respiratory rate ≥ 30 per minute, heart rate ≥ 125 per minute, SpO₂ $\leq 93\%$ on room air at sea level or PaO₂/FiO₂ < 300 mm Hg)
- Respiratory failure (defined as needing high-flow oxygen, noninvasive ventilation, mechanical ventilation or ECMO)
- Evidence of shock (SBP < 90 mm Hg, DBP < 60 mm Hg, or requiring vasopressors)
- Significant acute renal, hepatic, or neurologic dysfunction
- Admission to an ICU
- Death

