8.4.7 Events of Clinical Interest

Selected serious and nonserious AEs are also known as ECIs and must be reported to the Sponsor.

Events of clinical interest for this study include:

1. An overdose of Sponsor's product, as defined in Section 8.5.
2. Any laboratory confirmed diagnosis of SARS-CoV-2 infection (virologically confirmed by PCR) and any resulting clinical sequelae will be reported as an ECI in study participants throughout the duration of the study. See Section 8.3.7 for further details.
3. Known exposure to a confirmed case of active SARS-CoV-2, defined as individual who has had close contact (< 1.5 meters for ≥ 15 minutes), will be reported as an ECI in study participants throughout the duration of the study
4. AEs \geq Grade 3 reported as a solicited AE on the VRC
5. Acute respiratory distress syndrome (ARDS)
6. Pneumonitis
7. Acute cardiac injury
8. Arrhythmias
9. Septic shock-like syndrome
10. Acute kidney injury
11. Vasculitis
12. New onset Autoimmune disease (AID)
13. Meningitis
14. Atypical measles
15. Anosmia

16. Dysgeusia
17. Encephalitis
18. Encephalopathy
19. Clinically significant arthralgias

The investigator should report all ECIs for the whole period of the study.

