9.4.1 Safety Endpoints

The safety analysis endpoints include:

Solicited injection-site AEs from Day 1 through Day 5 after study intervention

Solicited systemic AEs from Day 1 through Day 14 after study intervention

Unsolicited AEs from Day 1 through Day 28 after study intervention

The broad AE categories consisting of any AE and any vaccine-related AE from Day 1 through Day 28 after study intervention

The broad AE categories consisting of any SAE, any vaccine related SAEs, and death from Day 1 through the duration of participation in the study

The broad AE categories consisting of any MAAE and any ECI (event of clinical interest) from Day 1 throughout the duration of the study.

Maximum temperature measurements meeting the Brighton Collaboration cut points from Day 1 through Day 14 after study intervention

Safety laboratory results, vital signs, and physical exam findings as described in the SoA

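### The Tier 2 row for any event of clinical interest mixes contact with a case and community infection with possible vaccine injury, which dilutes the V591–placebo contrast; confirmed infection is also defined two ways

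*Combined protocol and SAP*

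**What the plan says.** Section 9.4.1 lists as a safety endpoint "The broad AE categories consisting of any MAAE and any ECI (event of clinical interest) from Day 1 throughout the duration of the study". Section 9.6.1 makes it Tier 2 ("any SAE, any vaccine-related SAE, any MAAEs, any ECI, and death will be considered Tier 2 events"), and Table 9 gives it one row with a between-group CI by the Miettinen-Nurminen method. Table 9 has vaccine-related versions of the AE and SAE rows but none for ECIs, so the row has no causality filter.

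Section 8.4.7 lists 19 ECIs. Item 2 is infection: "Any laboratory confirmed diagnosis of SARS-CoV-2 infection (virologically confirmed by PCR) and any resulting clinical sequelae will be reported as an ECI". Item 3 is contact: "Known exposure to a confirmed case of active SARS-CoV-2, defined as individual who has had close contact". The same list holds possible vaccine harms such as ARDS, acute cardiac injury and encephalitis, and, as item 4, solicited reactions at or above "Grade 3 reported as a solicited AE on the VRC".

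Elsewhere the protocol keeps these ideas apart. Section 3 has exposure as its own exploratory endpoint ("Known exposure to a confirmed case of active SARS-CoV-2 reported as an ECI"), and confirmed infection as another. Stopping rule 3 in Section 6.7.1 names 12 ECI types, requires relatedness, and includes neither exposure nor infection.

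On what counts as infection, Section 4.2.1.3 says "Any laboratory confirmed diagnosis of SARS-CoV-2 infection (PCR or antigen based) and any resulting clinical sequelae will be reported as an ECI". Section 8.3.7 says "a virologically confirmed SARS-CoV-2 infection is defined as any study participant with positive SARS-CoV-2 PCR test", and item 2 of Section 8.4.7 also specifies PCR.

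**The concern.** Section 8.4.7 introduces ECIs as a selection of adverse events, and the SAP treats the row as a broad AE category. Under Section 10.3.1 an AE is something medically unfavourable that happens to the participant. Having stood near an infected person is not that. Community infection is an illness, but its frequency depends largely on local transmission. Counting either one makes a participant positive on this row whether or not anything else happened.

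At stake is the only planned summary that adds up the ECIs as a class. Injury-type ECIs may be spread over many terms, and a specific term gets a CI only if at least 4 participants in some group have it. Below that it is Tier 3, with point estimates alone. If the aggregate row is filled with background events, the safety review has no undiluted total to read.

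The two infection definitions matter separately. A participant positive only by antigen test is a case under Section 4.2.1.3 and not under Sections 8.3.7 and 8.4.7, so the infection count depends on which section is followed.

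**Working it through.** **The plan's own figure.** None is given for *any ECI*. The nearest is Table 11 (80% probability, two-sided 5%, labelled 228 V591 and 57 placebo). By the usual two-proportion formula with pooled null variance, its row of 11.2% against 2% gives power 0.605 at the labelled sizes and 0.801 with the two arm sizes interchanged; the other rows also return about 0.80 only when interchanged. That is a separate matter, but it means Table 11 cannot serve as the benchmark here.

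**Inputs.**
- Arm sizes from Section 9.1 and Tables 3 and 4: V591 2×4 + 10×20 = 208; placebo 2×1 + 10×5 = 52. (Section 9.9 uses 228 and 57.)
- Interval: Miettinen-Nurminen, 95%, from Section 9.6.1.
- Risk of an ECI other than items 2 and 3, assumed: q₁ = 10% on V591, q₀ = 2% on placebo.
- Background risk b of exposure or infection, equal in both arms and independent of other ECIs, assumed: 0 to 30%. The documents give no rate. The 3.4% value is an assumed 20% twelve-month risk cut to 56 days: 1 − 0.8^(56/365) = 0.034.

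**Composite risk.** P = 1 − (1 − q)(1 − b), so P₁ − P₀ = (1 − b)(q₁ − q₀). Background shrinks the difference by the factor 1 − b and raises both proportions, which widens the interval.

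**Chance that the CI lies above zero.** The lower limit exceeds zero when z = (x₁/208 − x₀/52) / √[p̄(1 − p̄)(1/208 + 1/52)(260/259)] is above 1.96, where p̄ = (x₁ + x₀)/260. Binomial probabilities are summed over every outcome (x₁, x₀) that meets this.

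| b | V591 % | Placebo % | Difference, points | 95% CI at expected proportions | Chance CI is above zero |
|---|---|---|---|---|---|
| 0 | 10.0 | 2.0 | 8.0 | −0.7 to 13.4 | 0.49 |
| 3.4% | 13.1 | 5.3 | 7.7 | −2.6 to 14.4 | 0.32 |
| 5% | 14.5 | 6.9 | 7.6 | −3.4 to 14.9 | 0.27 |
| 15% | 23.5 | 16.7 | 6.8 | −6.6 to 17.0 | 0.17 |
| 30% | 37.0 | 31.4 | 5.6 | −9.4 to 18.7 | 0.11 |

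**Other assumed effects.** These use the two-proportion formula at 208 and 52, with b = 0, 5, 10, 20 and 30%. For 10.3% against 0.1%, power is 0.80, 0.45, 0.32, 0.20 and 0.15. For 19.8% against 5%, it is 0.80, 0.63, 0.51, 0.36 and 0.27.

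**No vaccine effect.** With q₁ = q₀ the expected difference is zero at every b, and the CI excludes zero 4% to 5% of the time. Background therefore creates no false signal in the pooled comparison.

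**The case against.** A reader might infer that the row follows the epidemic instead of the vaccine. It can for the absolute percentage, but not for the comparison: allocation is 4:1 within every panel, so background is balanced in expectation. The late start of Panels K and L (Section 4.1) does not change that, because each has its own placebo participants. A shift would arise only if a single dose group were set against placebo pooled over panels, and the plan does not say whether it will do this for safety. As an illustration on the full schedule with an assumed 20% twelve-month risk, Panel F (534 days) would show 27.9% background against 22.9% in pooled placebo.

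A reader might also infer that background turns a clear signal into a null one. An unpooled Wald calculation suggests so: for 10% against 2%, z is 2.81 without background and 1.78, 1.14 and 0.77 at 5%, 15% and 30%. The plan does not use that interval. By its own method z is 1.86 without background and the CI already includes zero, so only a loss of probability can be claimed.

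Three further points carry weight:
- Tier 2 CIs are declared descriptive, and no decision rule uses this row.
- Solicited AEs, any SAE, vaccine-related AEs and SAEs, and death have their own rows, and stopping rule 3 has its own list, so an injury signal has other ways to be seen. None of these is an undiluted total of ECIs.
- The high background values are doubtful. Entry requires social distancing and excludes high-exposure occupations, and Amendment 04 brings the final visit forward to at least 56 days after the last vaccination.

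Finally, infection is not mere noise: Section 2.3 says that vaccine-enhanced disease has not been evaluated preclinically. That argues for showing infection separately, not for dropping it.

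**Conclusion.** The point holds as one of dilution and definition. *Any ECI* as specified combines a non-event (contact), a mainly community-driven illness and possible vaccine injuries, and the protocol's own Section 3 and stopping rule 3 keep these apart. In the worked case even a 3.4% background takes the chance of a CI above zero from 0.49 to 0.32, and 30% takes it to 0.11. These figures rest on assumed ECI risks, an assumed background equal in both arms, independence, and 208 and 52 evaluable participants. The direction does not depend on the particular values; the size does.

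The documents do not support a claim that the pooled comparison is biased, or that a vaccine-injury signal would go unseen across all planned outputs. The mismatch in the infection definition is established by the text alone; it affects participants who are positive by antigen test only.

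**What to change.** In Sections 9.4.1 and 9.6.1 and Table 9:
- Replace *any ECI* by a Tier 2 row for any ECI excluding items 2 and 3 of Section 8.4.7.
- Add confirmed SARS-CoV-2 infection as its own Tier 2 row.
- Give known exposure as a descriptive count without a CI.
- Count an event listed in its own right, such as ARDS, in the ECI row whatever the participant's infection status, and flag those in infected participants. No event is then reassigned after a test result is known.
- State whether dose-group safety comparisons use within-panel or pooled placebo.

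Reconcile the definition of laboratory-confirmed infection across Sections 4.2.1.3, 8.3.7 and 8.4.7, and list antigen-only positives separately so that the count can be read either way.

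The ECI type is already reported, so this needs one derived flag and no new data. The downside is one more unadjusted descriptive CI. Section 9 allows non-confirmatory changes in the supplemental SAP before unblinding; after that, label the split as post hoc.

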9.6.2 Statistical Methods for Immunogenicity Analyses

This section describes the statistical methods that address the secondary immunogenicity objectives. Methods related to exploratory objectives will be further described in the supplemental statistical analysis plan.

The geometric mean ratios and 95% CIs of the anti-SARS-CoV-2 spike serum nAb GMTs will be calculated using a cLDA method proposed by Liang and Zeger (2000) [Liang, K-Y and Zeger, S. L. 2000]. In this model, the response vector consists of the log-transformed prevaccination and postvaccination antibody titers. The repeated measures model will include terms for time, the interaction of time-by-vaccination group (with a restriction of the same baseline mean across groups). The treatment difference in terms of a geometric mean ratio at a given postvaccination time point will be estimated and tested from this model. The term for time will be treated as a categorical variable. An unstructured covariance matrix will be used to model the correlation among repeated measurements. This model allows the inclusion of participants who are missing either the baseline or postbaseline measurements, thereby increasing efficiency.

The observed nAb GMTs at each timepoint with serum collection and GMFRs from prevaccination to postvaccination will be performed within each vaccination group separately. Descriptive statistics with point estimates and within-group 95% CIs will be provided. The point estimates will be calculated by exponentiating the estimates of the mean of the natural log values and the within-group CIs will be derived by exponentiating the bounds of CIs of the mean of the natural log values based on the t-distribution.

A similar statistical approach will be used to evaluate the anti-SARS-CoV-2 spike serum IgG responses.

For responses smaller than the lower limit of quantitation (LLOQ), half of the LLOQ will be used for analysis when calculating the nAb GMTs and IgG GMCs.

A detailed analysis strategy for key immunogenicity endpoints is listed in [Table 10](#).

Table 10 Analysis Strategy for Immunogenicity Variables

Endpoint/Variable (Description, Time Point)	Primary vs. Supportive Approach ^a	Statistical Method	Analysis Population	Missing Data Approach
Secondary Endpoint				
nAb GMT ratio and IgG GMC ratio at Day 29 (all panels) and Day 85 (2-dose panels only)	P/S	cLDA model ^b (estimate and 95% CI)	PP/FAS	Model-based
nAb GMT and IgG GMC at all timepoint with serum collection	P	Descriptive Statistics (estimate, 95% CI)	PP	Missing data will not be imputed
GMFR from baseline to postvaccination for nAb and IgG	P	Descriptive Statistics (estimate, 95% CI)	PP	Missing data will not be imputed
CI = confidence interval; FAS = Full Analysis Set; GMC = geometric mean concentration; GMFR=geometric mean foldrise; GMT = geometric mean titer; IgG = Immunoglobulin G; nAb = neutralizing antibody; PP = Per-Protocol. ^a P = Primary approach; S = Supportive approach. ^b Estimation of the GMT ratios and computation of the corresponding 95% CIs will be calculated using t-distribution with the variance estimate from a constraint longitudinal data model (cLDA) utilizing the log-transformed antibody titers as the response and a single term for vaccination group.				

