In Part 2B, approximately 150 healthy older participants (aged > 55 years) will be enrolled in six Panels. Two Panels of older participants, Panel G and Panel H, will be administered a single dose of either $1 \cdot 10^5$ TCID₅₀ or $1 \cdot 10^6$ TCID₅₀ of V591. Two Panels of older participants, Panel I and Panel J, will be administered two doses of either $1 \cdot 10^5$ TCID₅₀ or $1 \cdot 10^6$ TCID₅₀ of V591 56 days apart. Two Panels of older participants, Panel K and Panel L, will be administered two doses of either $1 \cdot 10^5$ TCID₅₀ or $1 \cdot 10^6$ TCID₅₀ of V591 168 days apart. Twenty-five participants will be randomized into each panel per dosing regimen to receive IM vaccination of V591 or placebo in a 4:1 ratio. Part 2B may initiate based upon siDMC recommendation as outlined below and may initiate simultaneously with Part 2A. Study participants in Panels I-L may receive their second dose of V591 based upon siDMC recommendation as outlined below. Panel G, Panel H, Panel I, and Panel J may be enrolled in parallel, while Panel K and Panel L will only commence recruiting study participants after Panel G, Panel H, Panel I, and Panel J are full enrolled.

In accordance with the FDA's "Development and Licensure of Vaccines to Prevent COVID-19, Guidance for Industry", the Sponsor will make efforts recruit a representative population for this Phase 1/2 study, particularly in the Panels of older adults as this is the only planned study in Phase 1 that will include this population. In order to facilitate the enrollment of diverse study population, particularly those that have been disproportional impacted by COVID-19 and historically underrepresented in vaccine trials, older adults in Part 2B will only be recruited in the United States.

The Sponsor's standing internal Data Monitoring Committee (siDMC) will review safety and tolerability data throughout this study, will evaluate safety data for the Safety Reviews following the first and second vaccinations in the sentinel Panels, and will be convened to evaluate available data if stopping rules are met. The siDMC is a standing, internal Sponsor committee established to monitor early phase clinical studies. Additional details are provided in Section 10.1.4.1 and in the siDMC charter.

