As participants in Panel A, Panel B, and the first 5 subjects in Panel E will be amongst the first to receive doses of $1 \cdot 10^5$ TCID₅₀, $1 \cdot 10^6$ TCID₅₀, and $1 \cdot 10^7$ TCID₅₀ V591 respectively, they will be required to be seronegative for SARS-CoV-2 as an additional precaution. Participants in the rest of the study will not be screened by serology for SARS-CoV-2 and thus will not be required to be seronegative for enrollment.

Doses of $1 \cdot 10^5$ TCID₅₀ and $1 \cdot 10^6$ TCID₅₀ will also be the only dose levels administered to older participants after they have been assessed to be well tolerated in younger adults based on data from this study or the COVID-19-101 study as outlined in Section 4.1. These are doses that are most likely to be both well tolerated and immunogenic in this population, and it is intended to only administer V591 doses that are generally well tolerated and anticipated to elicit an immune response against SARS-CoV-2 in older participants. Two dose regimens of V591 will be given either 8 or 24 weeks apart in Panels of adults > 55 years of age. As older adults have historically demonstrated weaker responses to vaccines [Weinberger, B. 2012], 2 dose regimens of V591 with wider intervals than the 4 week interval in the COVID-19-101 study will be evaluated in an effort to identify a regimen of V591 that displays enhanced immunogenicity in older adults. This design will minimize the risks to older participants while efficiently obtaining immunogenicity data in this older population that is at greatest risk for severe COVID-19 disease.

In an previous Phase 1 study, MV-CHIK 101, that explored doses ranging from $1.5 \cdot 10^4$ to $3 \cdot 10^5$ TCID₅₀ of MV-CHIK in healthy adults, Doses of $7.5 \cdot 10^4$ and $3 \cdot 10^5$ TCID₅₀ MV-CHIK were generally immunogenic after a single vaccination, while the lower dose of $1.5 \cdot 10^4$ TCID₅₀ required 2 doses for comparable immunogenicity. Based on this clinical data, it is anticipated that a single dose of V591 greater than $7.5 \cdot 10^4$ TCID₅₀ may provide adequate immunogenicity after a single dose. Thus a single dose of $1 \cdot 10^5$ TCID₅₀ will be the lowest dose administered as a single dose regimen in this trial.

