6.3.2 Stratification

No stratification based on age, sex, or other characteristics will be used in this study. Based on the study design, intervention allocation/randomization will automatically be stratified according to participant's age at time of randomization (18 to 55 and > 55 years of age).

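### The immunogenicity model has no age term and leaves vaccination group undefined; if groups are dose levels pooled across ages, reading 10^4 or 10^7 against 10^5 or 10^6 is confounded by age

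*Combined protocol and SAP*

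**What the plan says.** Section 9.6.2 gives the constrained longitudinal model (cLDA) for neutralising titres, and by extension IgG: "The repeated measures model will include terms for time, the interaction of time-by-vaccination group (with a restriction of the same baseline mean across groups". Footnote b of Table 10 describes it as "utilizing the log-transformed antibody titers as the response and a single term for vaccination group". Neither mentions age. The descriptive GMTs and fold rises "will be performed within each vaccination group separately", again without an age split. The supplemental plan is not assigned this analysis: "Methods related to exploratory objectives will be further described in the supplemental statistical analysis plan", whereas the GMT and GMC ratios are secondary.

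Age is built into the design. Each panel holds one age group, so Section 6.3.2 can say that "intervention allocation/randomization will automatically be stratified according to participant's age at time of randomization" (18 to 55, or over 55). Older adults receive only 10^5 and 10^6 TCID50; 10^4 (Panel F) and 10^7 (Panel E) are given to younger adults only. Section 4.2.6 expects an age effect: "As older adults have historically demonstrated weaker responses to vaccines".

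**The concern.** The trial ranges over dose in two age groups, and Section 4.3.1 names finding the dose that reaches the target immune response as an aim. A reader will therefore set the dose-level estimates side by side. If each is an average over whatever ages received that dose, differences between dose levels mix the effect of dose with the effect of age. Two things would be at stake at Day 29: a false dose pattern, and the absence of any V591/placebo ratio for older adults, the population for which the longer-interval regimens were added. Termination does not remove the issue, because Amendment 04 still provides for a final analysis.

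**Working it through.** **1. Which groups does the plan compare?** The only worked immunogenicity comparison is Table 13. Its form is ratio × exp(± t(0.975, n1+n0−2) × SD × √(1/n1 + 1/n0)).

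- Inputs: 85% evaluable (Section 9.9.2); 84 per dose level for 10^5 and 10^6, and 57 placebo (Table 12). In whole participants, 71 and 48.
- At SD 1.0: √(1/71 + 1/48) = 0.1869; t(117) = 1.980; half-width 0.370. Ratio 1.5 gives (1.04, 2.17) and ratio 3.0 gives (2.07, 4.34), as printed. All 12 cells match.
- Other pairings fail. Randomised counts of 228/57, 208/52, 20/57, 24/57 (younger), 60/57 and 60/30 (older), and 20/5 (single panel) match none of the 12 cells under any rounding. Using the current 52 placebo, 84/52 matches at most one; 71 vs 44 gives (1.03, 2.19) for the first cell.

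So Table 13 was built from one dose level with both ages pooled, against all placebo pooled.

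**2. Age mix of those groups**, counted from Tables 3 and 4:

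| Group | Younger | Older | Older share |
|---|---|---|---|
| 10^4 (Panel F) | 20 | 0 | 0% |
| 10^5 | 4 + 20 = 24 | 60 | 71.4% |
| 10^6 | 4 + 20 = 24 | 60 | 71.4% |
| 10^7 | 20 | 0 | 0% |
| Placebo | 2 + 20 = 22 | 30 | 57.7% |
| All V591 | 88 | 120 | 57.7% |

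**3. Size of the confounding.** Let r be the younger:older ratio of geometric mean response, with no dose effect. The 10^5 log mean is (24/84)·μ_Y + (60/84)·μ_O and the 10^7 log mean is μ_Y. The apparent 10^7/10^5 ratio is therefore r^(60/84) = r^0.714. The documents give no value for r, so a range is assumed:

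| Assumed r | 1.25 | 1.5 | 2 | 3 |
|---|---|---|---|---|
| Spurious 10^7/10^5 | 1.17 | 1.34 | 1.64 | 2.19 |

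A simulation (2,000 runs; baseline-adjusted ANCOVA standing in for a two-time-point cLDA) agrees. With a true V591/placebo ratio of 3.0 at every dose in younger adults and responses halved in older adults, the model without age gave 3.00, 1.82, 1.83 and 3.01 for 10^4, 10^5, 10^6 and 10^7. With age terms, the younger-adult estimates were 3.02, 3.02, 3.04 and 3.03.

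**4. Precision if age is respected** (SD 1, 85% evaluable, current 52 placebo; log half-width = t × √(1/n1 + 1/n0)):

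- 10^7: all placebo, 17 vs 44, 0.571; younger placebo only, 17 vs 19, 0.678 (+19%).
- 10^5 or 10^6: pooled, 71 vs 44, 0.380; younger only, 20 vs 19, 0.649 (+71%).
- At ratio 2.0 for 10^5, using unrounded evaluable counts: younger only (1.05, 3.83); older only (1.23, 3.24).
- Age-stratified combined 10^5 or 10^6, inverse-variance weights on unrounded counts: younger 1/(1/20.4 + 1/18.7) = 9.76; older 1/(1/51 + 1/25.5) = 17.00; SE = 1/√26.76 = 0.193. The pooled SE is √(1/71 + 1/44) = 0.192 (0.191 with unrounded counts).

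**The case against.** **The pooling is inferred.** This stands. Table 12 is a count of who is due to receive what, not a definition of analysis groups, and Table 13 is a precision illustration. Both carry 57 placebo, and Table 12 also lists a 125-fold dilution group; neither belongs to the current design of 208 V591 and 52 placebo. The secondary objective is indexed by panel. If *vaccination group* meant panel, no V591 group would mix ages, although a single-age panel set against pooled placebo (58% older) would still differ in age mix.

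**No cross-dose ratio is planned.** Also correct. Table 10 lists V591/placebo ratios, and the study is descriptive. A reader might infer that these planned ratios are themselves biased. The documents do not show that: if placebo titres do not depend on age (an assumption), 10^7/placebo is a valid younger-adult ratio and 10^5/placebo a valid mixed-age one. The trouble starts when the two are read against each other.

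**Not every comparison is affected.** A reader might conclude that the whole dose-response is confounded. It is not: 10^5 and 10^6 have the same age mix, as do all V591 and all placebo. At Day 85 in Panels A, B, I and J, 10^5 and 10^6 are each 20/24 older and placebo 10/12, so those are balanced too.

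**The common baseline.** Randomisation secures equal baseline means only within a panel, only sentinels are screened by serology, and "Panel K and Panel L will only commence recruiting study participants after Panel G, Panel H, Panel I, and Panel J are full enrolled". It is tempting to call the constraint invalid. But criterion 2 excludes confirmed prior infection in every panel, and if most participants are seronegative at entry the effect is small. The documents give nothing to size it, so it is secondary.

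**Conclusion.** The concern holds in a bounded form. The model has no age term, no age-specific ratio is planned, and the grouping is undefined; these are matters of text. If groups are dose levels pooled across ages, as Tables 12 and 13 indicate, Day 29 readings of 10^4 or 10^7 against 10^5 or 10^6 carry a spurious factor of r^0.714: 1.17 to 2.19 for assumed r of 1.25 to 3. The direction follows from the protocol's own expectation about older adults; the size rests on r, which it does not give. The age mix uses planned numbers and equal evaluability across panels, so it should be recounted on the participants actually enrolled. No type I error claim is touched, since nothing is formally tested; the risk is misleading estimates.

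**What to change.** In Section 9.6.2 and Table 10:

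- Define *vaccination group* in words for each time point, and bring Tables 12 and 13 into line with the current design.
- Fit the cLDA separately in younger adults (Parts 1 and 2A; 22 placebo) and older adults (Part 2B; 30 placebo), with the baseline mean constrained equal within each stratum. An equivalent single model should use only the age-by-dose cells that exist: a full age-by-group-by-time interaction has empty cells, because no older adult receives 10^4 or 10^7.
- Report V591/placebo ratios and descriptive GMTs by age stratum, plus an age-stratified combined ratio for 10^5 and 10^6 with its weights stated.
- Compare 10^4 and 10^7 with the other doses in younger adults only.

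No data collection changes. This is more than adding one covariate, but it remains a revision of analysis text and programming. The price is the wider age-specific intervals shown above, largest for 10^5 and 10^6 in younger adults. The combined ratio keeps nearly all the precision of the pooled one.
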